## 15.1. EXPLORATORY ANALYSIS

CCI [REDACTED]

## 16. SAFETY OUTCOMES

There will be no statistical comparisons between the treatment groups for safety data, unless otherwise specified with the relevant section.

### 16.1. ADVERSE EVENTS

Adverse Events (AEs) will be coded using Medical Dictionary for Regulatory Activities (MedDRA) central

---

Document:	\\usadc-nas01a\cp_ops\PROJECTS\Glaxo SmithKline\GSK208109_BZA47109\SAP		
Author:	PPD [REDACTED]	Version Number:	3.0
		Version Date:	27SEP2021

Template No: CS\_TP\_BS016 – Revision 5  
Effective Date: 01Apr2018

Reference: CS\_WI\_BS005

---

coding dictionary, Version 22.0.

The percentage of subjects with at least 1 local AE (solicited and unsolicited), with at least 1 general AE (solicited and unsolicited) and with any AE during the 7-day or the 30-day follow-up period will be tabulated with exact 95% CI after each vaccination and overall.

The percentage of doses followed by at least 1 local AE (solicited and unsolicited), by at least 1 general AE (solicited and unsolicited) and by any AE will be tabulated, overall vaccination course, with exact 95% CI. The same computations will be done for Grade 3, any AEs considered related to vaccination, any Grade 3 AEs considered related to vaccination and any AEs resulting in a medically attended visit.

The percentage of subjects/doses reporting each individual solicited local and general AE during the 7-day follow-up period will be tabulated with exact 95% CI as follows:

- Over the 2 or 3 doses, the percentage of subjects with the symptom and its exact 95% CI.
- Over the 2 or 3 doses, the percentage of doses with the symptom and its exact 95% CI.
- At each study dose (visit), the percentage of subjects with the symptom and its exact 95% CI.

Occurrence of fever will be reported per 0.5°C cumulative increments as from  $\geq 38^{\circ}\text{C}$  as well as the occurrence of fever  $>40^{\circ}\text{C}/104^{\circ}\text{F}$  with causal relationship to the study treatment.

The verbatim reports of unsolicited symptoms will be reviewed by a physician and the signs and symptoms will be coded per the Medical Dictionary for Regulatory Activities (MedDRA). Every verbatim term will be matched with the appropriate preferred term. The percentage of subjects with unsolicited AEs within 30 days after any doses with its exact 95% CI will be tabulated by group and by MedDRA preferred term. Similar tabulation will be done for Grade 3 unsolicited AEs, for unsolicited AEs that resulted in a medically attended visit, for Grade 3 and causally related unsolicited AEs and for unsolicited AEs causally related to vaccination. These tabulations will include SOC and SOC/PT analyses.

The number of subjects who experienced at least 1 SAE or any AE of specific interest (potential immune mediated disease) within 30 days after any dose, from dose 1 until 30 days post last dose and during the entire study period will be reported.

The following summaries for COVID-19 infections will be presented:

- Number of subjects with an AE of suspected, probable or confirmed assessment of COVID-19 infection
- Number of subjects who had a COVID-19 diagnosis test performed and the number of subjects with positive, negative or indeterminate results
- Incidence of COVID-19 as AEs and SAEs
- Summary of severity, duration and outcome of AEs related to COVID-19
- Incidence of AEs over the course of trial (pre and during pandemic)
- Incidence of AEs by age and gender over the course of trial (pre and during pandemic)

---

Document: \\usadc-nas01a\cp\_ops\PROJECTS\Glaxo SmithKline\GSK208109\_BZA47109\SAP  
Author: PPD

Version Number: 3.0  
Version Date: 27SEP2021

Template No: CS\_TP\_BS016 – Revision 5  
Effective Date: 01Apr2018

Reference: CS\_WI\_BS005

Events observed on or after 01DEC2019 will be deemed to occur during the pandemic while the events observed prior to 01DEC2019 will be considered pre-pandemic.

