3.0 OBJECTIVES AND ENDPOINTS

Table 9 Study Objectives and Endpoints

Objectives	Endpoints

Primary
 
 To evaluate the safety and reactogenicity profile of the C. difficile F2 fusion protein when administered with or without AS01B adjuvant as IM doses according to a 0, 1-month schedule, in healthy adults aged between 18-45 years and between 50-70 years followed by an additional dose administered approximately 15 months after Dose 2 in a subcohort of subjects aged 50-70 years, during the entire study period. 	
 Solicited local and general symptoms. 
 Occurrence of solicited local symptoms (any and Grade 3) within 7 days (Day 1 to Day 7) after each vaccination, in all subjects and in all groups. Occurrence of solicited general symptoms (any, Grade 3, related, and Grade 3 related) within 7 days (Day 1 to Day 7) after each vaccination, in all subjects and in all groups. Unsolicited AEs. 
 Occurrence of unsolicited AEs (any, Grade 3, related, Grade 3 related, and those resulting in a medically attended visit) within 30 days (Day 1 to Day 30) after each vaccination, according to the MedDRA classification, in all subjects and in all groups. SAEs. 
 Occurrence of SAEs from Dose 1 (Day 1) up to study end, in all subjects and in all groups. AEs of specific interest. 
 Occurrence of AEs of specific interest (pIMDs) from Dose 1 up to study end, in all subjects and in all groups. Laboratory parameters 
 Occurrence of hematological (white blood cells, platelets count, and hemoglobin level) and biochemical (alanine aminotransferase, aspartate aminotransferase, creatinine, and uric acid) laboratory abnormalities at Screening, Days 8, 31, 38, 180, 390, 476, 491, 498, and 670 and urinary laboratory abnormalities (protein, glucose, and blood) at Screening. (Grades will be based on the local laboratory normal ranges and derived from the FDA Toxicity Grading Scale for laboratory abnormalities).

Table 9 Study Objectives and Endpoints

Objectives	Endpoints
Secondary	

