4.0 STUDY DESIGN

4.1 Overall Design

Protocol waivers or exemptions are not allowed unless necessary for the management of immediate safety concerns. Therefore, adherence to the study design requirements, including those specified in the outline in the schedule of activities (Section 1.3), are essential and required for study conduct.

This is a Phase I, first-in-human, single-center, randomized, observer-blind, placebo-controlled, study with 2 to 3 treatment groups per step in a 4-step staggered design in healthy subjects to generate safety, reactogenicity, and immunogenicity data for the development of a candidate *C. difficile* vaccine that would protect against primary cases of CDI and CDI recurrence.

The duration of the study for each subject receiving 2 doses will be approximately 1 year and for each subject receiving 3 doses will be of approximately 2 years.

Primary completion date (PCD): Visit 11 (Day 670) (refer to [Appendix 2](#) for the definition of PCD).

Study conclusion for individual subjects: The study conclusion for subjects receiving 2 doses will be Visit 7 (Day 390) and for subjects receiving 3 doses will be Visit 11 (Day 670) (refer to [Appendix 2](#) for the definition of EoS).

A 4-step staggered design will be used to ensure maximum safety of the participating subjects (see [Figure 1](#)):

- **Step 1:** Vaccination of approximately 20 subjects aged 18-45 years (approximately 10 subjects in the CDIFF antigen [Ag] group and approximately 10 subjects in the placebo group). An internal safety review committee (iSRC) will review all accumulating safety data after Dose 1 and then again after Dose 2. Vaccination in Step 2 will proceed in the absence of a safety concern detected by the iSRC on all accumulating safety data at the end of Step 1.
- **Step 2:** Vaccination of approximately 20 subjects aged 50-70 years (approximately 10 subjects in the CDIFF Ag group and approximately 10 subjects in the placebo group). An iSRC will review all accumulating safety data after Dose 1 and then again after Dose 2. Vaccination in Step 3 will proceed in the absence of a safety concern detected by the iSRC on all accumulating safety data at the end of Step 2.

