- **Step 3:** Vaccination of approximately 30 subjects aged 50-70 years (approximately 10 subjects in the CDIFF Ag group, approximately 10 subjects in the CDIFF Ag + an adjuvant system containing 3-O-desacyl-4'-monophosphoryl lipid A [MPL], QS-21 and liposome [50 µg MPL and 50 µg QS-21] AS01B group, and approximately 10 subjects in the placebo group). An iSRC will review all accumulating safety data after Dose 1, and then after Dose 2. Vaccination in Step 4 will proceed in the absence of a safety concern detected by the iSRC on all accumulating safety data at the end of Step 3.

- **Step 4:** Vaccination of approximately 70 subjects aged 50-70 years (approximately 25 subjects in the CDIFF Ag group, approximately 35 subjects in the CDIFF Ag + AS01_B group, and approximately 10 subjects in the placebo group). An iSRC will review all accumulating safety data 3 weeks after the start of vaccination in Step 4 and then about every 3 weeks until all subjects have received Dose 1. In addition, the iSRC will review all safety data after Dose 2 (refer to Section 8.11 for study procedures to be considered during special circumstances). A subcohort of subjects who have successfully completed all visits up to Visit 7, have received two doses on an active arm (ie, the subjects who received placebo will be excluded), do not meet any contraindication for subsequent vaccination, and still meet the eligibility criteria will receive a third dose after the iSRC has reviewed all the accumulating safety data at the end of Step 4 Dose 2. If there are any safety concerns observed during SRT reviews post Dose 3, an ad hoc iSRC meeting will take place to review the unblinded safety data.

Refer to Section 9.6 for iSRC oversight.

During all 4 steps, all subjects should be closely observed for at least 60 minutes after vaccination.

For Steps 1, 2, and 3 only, all subjects should be vaccinated sequentially and at least 60 minutes apart to allow for monitoring of any acute events (eg, hypersensitivity reaction).

During vaccination days of Steps 1, 2, and 3 (ie, Day 1 and Day 31), vaccination will be limited to a maximum of 10 subjects per day. In Step 4, there is no limit related to the number of subjects to be vaccinated per day.

Table 10 Study Groups Foreseen in the Study (Refer to Section 8.11 for Study Procedures to be Considered During Special Circumstances)

Step	Study Groups	Number of Subjects	Age (Minimum/Maximum)
1	Placebo	10	18-45 years
	CDIFF Ag	10	18-45 years

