4.2.2 Rationale for Randomization and the Use of Placebo

Randomized, placebo-controlled studies are widely considered to be the most rigorous method for the efficacy evaluation of treatments or prevention interventions. To be ethical, clinical

research requires balancing rigorous science with the protection of subjects. The use of placebo controls in studies for conditions with no effective treatment is widely accepted.⁶ Up to date, there is no established standard of care to prevent CDI.

Likewise, the Declaration of Helsinki allows placebo controls and states: “Where for compelling and scientifically sound methodological reasons the use of placebo is necessary to determine the efficacy or safety of an intervention and the patients who receive placebo will not be subjected to additional risks of serious or irreversible harm.”⁷

Randomization is used to reduce bias of selection and the placebo group is included as a control for the reactogenicity, the safety and the immunogenicity assessments.

The third dose of the vaccine is being given to the subjects recruited in the active groups of the last step of the study, to demonstrate if a similar kinetics in terms of anti-Toxin A/Toxin B can be achieved with the F2 antigen formulation with or without an adjuvant. Therefore, the third dose will not be given to the subjects receiving placebo.

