9.4.2 Safety Analyses

9.4.2.1 Primary Analyses

The primary analysis will be performed on the Exposed Set.

The percentage of subjects with at least 1 local AE (solicited and unsolicited), with at least 1 general AE (solicited and unsolicited) and with any AE during the 7-day or the 30-day follow-up period will be tabulated with exact 95% CI after each vaccination and overall. The percentage of doses followed by at least 1 local AE (solicited and unsolicited), by at least 1 general AE (solicited and unsolicited) and by any AE will be tabulated, overall vaccination course, with exact 95% CI. The same computations will be done for Grade 3, any AEs considered related to vaccination and any Grade 3 AEs considered related to vaccination.

The percentage of subjects/doses reporting each individual solicited local and general AE during the 7-day follow-up period will be tabulated with exact 95% CI as follows:

- Over the 2 or 3 doses, the percentage of subjects with the symptom and its exact 95% CI.
- Over the 2 or 3 doses, the percentage of doses with the symptom and its exact 95% CI.
- At each study dose (visit), the percentage of subjects with the symptom and its exact 95% CI.

Occurrence of fever will be reported per 0.5°C cumulative increments as from $\geq 38^{\circ}\text{C}$ as well as the occurrence of fever $>40^{\circ}\text{C}/104^{\circ}\text{F}$ with causal relationship to the study treatment.

The verbatim reports of unsolicited symptoms will be reviewed by a physician and the signs and symptoms will be coded according to the Medical Dictionary for Regulatory Activities (MedDRA). Every verbatim term will be matched with the appropriate preferred term. The percentage of subjects with unsolicited AEs within 30 days after any doses with its exact 95% CI will be tabulated by group and by MedDRA preferred term. Similar tabulation will be done for Grade 3 unsolicited AEs, for unsolicited AEs that resulted in a medically attended visit, for Grade 3 and causally related unsolicited AEs and for unsolicited AEs causally related to vaccination.

The number of subjects who experienced at least 1 SAE or any AE of specific interest (pIMD) during the entire study period will be reported.

For each group and for each hematology, biochemistry, and urinalysis parameter:

- The percentage of subjects having hematology, biochemistry, and urinalysis results below or above the local laboratory normal ranges will be tabulated by timepoint.

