
 • All solicited AEs during 7 days following administration of each dose of study vaccine(s) (Day 1 to Day 7) must be recorded in the eCRF, irrespective of intensity or whether or not they are considered vaccination-related. • All other AEs during 30 days following administration of each dose of study vaccine(s) (Day 1 to Day 30) must be recorded in the appropriate section of the eCRF, irrespective of intensity or whether or not they are considered vaccination-related. • The time period for collecting and recording SAEs will begin at the first receipt of study vaccine(s) and will end 359 days following administration of the last dose of study vaccine(s) for each subject receiving 2 doses and 6 months following administration of the last dose of study vaccine(s) for each subject receiving 3 doses. See “Reporting of Serious Adverse Events, Pregnancies, and Other Events” for instructions on reporting of SAEs. • All AEs/SAEs leading to withdrawal from the study will be collected and recorded from the time of the first receipt of study vaccine. • In addition to the above-mentioned reporting requirements and in order to fulfil international reporting obligations, SAEs that are related to study participation (ie, protocol-mandated procedures, invasive tests, a change from existing therapy) or are related to a concurrent GSK medication/vaccine will be collected and recorded from the time the subject consents to participate in the study until she/he is discharged from the study. • The time period for collecting and recording pregnancies will begin at the first receipt of study vaccine(s) and will end 359 days following administration of the last dose of study vaccine(s) each subject receiving 2 doses and 6 months following administration of the last dose of study vaccine(s) for each subject receiving 3 doses. See “Reporting of Serious Adverse Events, Pregnancies, and Other Events” for instructions on reporting of pregnancies. • The time period for collecting and recording of AESIs will begin at the first receipt of study vaccine(s) and will end 359 days following administration of the last dose of study vaccine(s) each subject receiving 2 doses and 6 months following administration of the last dose of study vaccine(s) for each subject receiving 3 doses. See “Reporting of Adverse Events of Specific Interest to GSK” for instructions on reporting of AESIs.
Evaluation of Adverse Events and Serious Adverse Events

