## 6.2. TREATMENT SUMMARIZATION

In general, data will be presented for each treatment group:

Age	Treatment
50-70 Y	CDIFF Ag + AS01 B
	CDIFF Ag
	Placebo
18-45 Y	CDIFF Ag
	Placebo

Data for all study subjects combined will also be presented when appropriate. Analysis by age in older adult cohort will be performed by age strata (50-59 years old and 60-70 years old) for the descriptive immunogenicity analyses if at least 6 subjects are available in these subgroups and in at least one active arm.

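### Ages 50-70: the whole-study SAE/pIMD count runs to Day 670 for Dose 3 recipients but to Day 390 for all placebo, with no common Day 390 cut or required Dose 3 to Day 670 SAE/pIMD table in the visible text

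*SAP*

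**What the plan says.** Protocol 3.0 defines the primary SAE endpoint as "Occurrence of SAEs from Dose 1 (Day 1) up to study end, in all subjects and in all groups", and words the pIMD endpoint the same way. Protocol 9.4.2.1 turns this into a count: "The number of subjects who experienced at least 1 SAE or any AE of specific interest (pIMD) during the entire study period will be reported". SAP 16.1 repeats it with two more windows, "within 30 days after any dose, from dose 1 until 30 days post last dose and during the entire study period will be reported".

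The end of follow-up depends on the number of doses (Protocol 4.1, study conclusion "for subjects receiving 2 doses will be Visit 7 (Day 390) and for subjects receiving 3 doses will be Visit 11 (Day 670"). The SAE collection period in Protocol Appendix 6 follows the same split: it "will end 359 days following administration of the last dose of study vaccine(s) for each subject receiving 2 doses and 6 months following administration" for those receiving 3 doses. The pIMD period has the same lengths.

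Only Step 4 active subjects can receive Dose 3. On placebo, Protocol 4.2.2 says: "Therefore, the third dose will not be given to the subjects receiving placebo". SAP 6.2 says "In general, data will be presented for each treatment group" and lists the groups by treatment within age stratum, so steps are pooled.

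Protocol 9.4.2.1 makes separate subcohort safety summaries optional. SAP 5.2.3 defines a Subcohort Exposed Set, but the analysis-by-set table in SAP 5.6, as far as it can be read, assigns no analysis to it.

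**The concern.** A whole-study count compares arms fairly only if they are observed for similar lengths of time. Here the longer window exists only on vaccine, and for a larger share of the adjuvanted arm (35/45) than of the unadjuvanted arm (25/45). Equal background rates would therefore produce percentages in the order adjuvanted, unadjuvanted, placebo. Safety is the primary objective, and Protocol Table 8 lists autoimmune disease as the theoretical risk tied to adjuvants, so this is the order a reader will be looking for. The contrast between the two active arms is affected as well as each contrast with placebo.

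Both SAP-only windows also lengthen with the number of doses. None of the three stops at a day common to all subjects.

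**Working it through.** **The plan's own figure.** The documents give no figure for the follow-up imbalance. The nearest safety figure is in Protocol 9.2: 45 subjects give 80% or 90% probability of seeing at least one event at true rates of 3.5% or 5.0%. 1 − 0.965^45 = 79.9% and 1 − 0.95^45 = 90.1%, so it reproduces.

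**Inputs from the documents.** Ages 50-70: 45 Ag+AS01B, 45 Ag, 30 placebo (Protocol 9.2). Step 4 active: 35 and 25 (Table 10). Elapsed days from Day 1: 389 to Day 390, 490 to Day 491 (Dose 3), 669 to Day 670. These days are nominal. Adding the shortest and longest Table 7 intervals puts Visit 7 between Day 381 (31+350) and Day 431 (36+395), and Visit 11 between Day 572 (31+350+20+1+170) and Day 786 (36+395+150+15+190).

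**Mean follow-up at full Dose 3 uptake.**
- Ag+AS01B: (35×669 + 10×389)/45 = 606.8 days
- Ag: (25×669 + 20×389)/45 = 544.6 days
- Placebo: 389 days

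**Assumptions not in the documents.** Constant hazard h, equal in all arms, at 2, 5 or 10 per 100 person-years; Dose 3 uptake u from 50% to 100%.

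**Model.** p(d) = 1 − exp(−h·d/365.25), and n3 = 35 or 25.
- Without selection: arm risk = p(389) + (n3·u/45)·[p(669) − p(389)].
- Full-selection bound (every SAE or pIMD before Day 491 bars Dose 3): replace the bracket by exp(−h·490/365.25)·p(179).

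**Example, h = 0.05.** p(389) = 5.186% and p(669) = 8.751%, a difference of 3.565 points.
- Ag+AS01B, u = 1, no selection: 5.186 + (35/45)×3.565 = 7.96%; ratio 1.535.
- Ag, same: 5.186 + (25/45)×3.565 = 7.17%; ratio 1.382.
- Ag+AS01B, u = 0.5, full selection: 5.186 + (17.5/45)×2.264 = 6.07%; ratio 1.170.

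| h per 100 person-years | Placebo risk | Ag+AS01B / Ag ratio, u = 1, no selection | Ag+AS01B ratio, u = 0.5, no selection | Ag+AS01B / Ag ratio, u = 0.5, full selection |
|---|---|---|---|---|
| 2 | 2.11% | 1.550 / 1.393 | 1.275 | 1.175 / 1.125 |
| 5 | 5.19% | 1.535 / 1.382 | 1.267 | 1.170 / 1.121 |
| 10 | 10.10% | 1.511 / 1.365 | 1.255 | 1.161 / 1.115 |

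**Subjects whose first event falls only in the extra time** (Ag+AS01B, u = 1, no selection): 35×[p(669) − p(389)] = 0.52 of 1.47, 1.25 of 3.58 and 2.32 of 6.87 expected, at h = 2, 5 and 10.

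**How often Ag+AS01B shows the higher percentage** (1,000,000 simulated trials, 45 v 30, u = 1, no selection): 56%, 66% and 73%, against 41%, 48% and 48% with equal windows to Day 390.

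**SAP-only rows, h = 5 per 100 person-years.**
- Dose 1 to 30 days after the last dose ends near Day 61 (60 days) or Day 521 (520 days). p(60) = 0.818% and p(520) = 6.871%. Ag+AS01B, u = 1, no selection: 0.818 + (35/45)×6.053 = 5.53%; ratio 6.8. Under full selection the added term is (35/45)·exp(−h·490/365.25)·p(30), and the ratio is 1.36 at u = 1 and 1.18 at u = 0.5.
- Within 30 days after any dose covers about 60 or 90 days. Mean windows are (35×90 + 10×60)/45 = 83.3 and (25×90 + 20×60)/45 = 76.7 days against 60, ratios 1.39 and 1.28.

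**After the fix.** Over Dose 1 to Day 390 all three groups have 389 nominal days and equal expected risk.

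**The case against.** The plan already contains much of what a reader needs. SAP 16.1 requires 7- and 30-day AE tables after each vaccination, Dose 3 included, and SAP 7.1.3 puts SAEs into unsolicited summaries unless otherwise specified. SAP 14 presents doses administered by treatment, so the imbalance in third doses will be visible. SAP 6.4.1 ties each event to the most recent dose, and SAP 16.1.2 lists SAEs. Safety concerns after Dose 3 go to an ad hoc unblinded iSRC review (Protocol 9.4.2.2). The first interim preceded Dose 3, and all previous analyses are to be re-produced at the end (Protocol 9.8, SAP 4.4), so its last-dose row gives an equal-window view to Day 61. SAP 16 plans no statistical comparison of safety unless a section specifies one.

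All of this stands, and it limits the point. A reader might infer that post-Dose 3 safety goes untabulated; the by-dose tables contradict that. A reader might infer a biased test or an inflated error rate; no safety test is planned. Nor can it be said that the outputs will lack a Day 390 cut: SAP 8 leaves table content to templates that are not visible.

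The safeguards still leave a gap. None gives SAE and pIMD counts on equal windows from Day 61 to Day 390, or a required count from Dose 3 to Day 670. Listings and dose attribution allow a reader to build these by hand; they do not supply them.

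**Conclusion.** The point holds as a cheap improvement. Following the stated rule gives SAE/pIMD windows of unequal length, in the order adjuvanted, unadjuvanted, placebo. With no vaccine effect, the expected apparent ratio to placebo is about 1.16 to 1.55 for Ag+AS01B and 1.12 to 1.39 for Ag. The direction follows from the documents; the size rests on the assumed hazard and uptake. The low ends combine 50% uptake with the assumption that every earlier event bars Dose 3. That bound is pessimistic, because the SAE- and pIMD-specific contraindications in Protocol 6.2 turn on relatedness or Investigator judgement.

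Two figures invite over-reading. The 6.8 for the last-dose row assumes full uptake and no selection, and should not be quoted without the 1.36 under full selection. Protocol Table 21 might be read as 50 of 60 receiving Dose 3, but it shows about 60 samples at Visit 8, the Dose 3 visit, and about 50 only at Visits 10 and 11. It does not state uptake.

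In subjects, the excess on Ag+AS01B is about 0.5 to 2.3 at full uptake without selection. Ages 18-45 and the per-dose reactogenicity tables are not affected.

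**What to change.** In SAP 16.1 and Protocol 9.4.2.1:

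1. Add the number and percentage of subjects with SAEs and with pIMDs, for all groups, over the common window Dose 1 to Visit 7 (Day 390).
2. Make mandatory at the final analysis an SAE/pIMD table from Dose 3 to Day 670, by active arm, on the Subcohort Exposed Set.
3. Keep the whole-study count, since it is the protocol endpoint, and the two SAP-only rows. Label each with follow-up time per arm.

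The cost is wording in the SAP, protocol and table shells, plus a few extra tables. No new data are needed. Producing the Dose 3 table by arm at the second interim could unblind individual subjects through small cells, a risk SAP 4.3 already recognises for the first interim. Deferring it to the final analysis avoids this.
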